13.6 Recording and Reporting of Adverse Events

All AEs, regardless of the relationship to IMP, occurring from the time written ICF will be obtained from a subject until the end of the safety Follow-up Period or the withdrawal of the subject from the study will be recorded.

NOTE: Elective hospitalization or procedure/surgery planned before subject enrollment for a preexisting medical condition does not constitute an AE unless the underlying disease or condition worsens after signing ICF.

All AEs will be recorded on an AE form in the eCRF. Reports should contain a description of the event, date of onset, date of resolution, severity, treatment required, relationship to IMP, action taken with the IMP, outcome and whether the event is classified as serious.

The Investigator will evaluate the severity of the AEs (as defined in Section 13.3) and will assess the causality between the AEs and the IMP (as defined in Section 13.4).

Pre-existing illnesses, which started prior to entry and are still ongoing at the start of the study, will not be considered AEs unless they worsen during the treatment period. Pre-existing conditions will be recorded as medical history.

If the Investigator becomes aware of any new safety information, or any safety information, which appears to be either study or IMP, related after the Final Follow-up period, then they must notify the Sponsor immediately.

13.7 Recording and Reporting of Serious Adverse Events

All SAEs occurring from the time written ICF is obtained from a subject until the end of the Safety Follow-up period or the withdrawal of the subject from the study must be

reported to the Sponsor within 24 hours of the Investigator becoming aware of the SAE. All SAEs must also be entered in the AE section of the eCRF as soon as possible.

SAE reports should be completed as thoroughly as possible, including an assessment of causality. All such reports will identify subjects by unique code numbers assigned to the study participants, rather than by the subjects' names, personal identification numbers, or addresses.

The Sponsor will comply with the applicable regulatory requirements related to the reporting of suspected unexpected serious adverse reactions (SUSARs) to the regulatory authorities and central IRBs. The Investigator will be responsible for informing the local IRBs of relevant safety information, including SUSARs, as per local laws and requirements.

13.8 Follow-up of Adverse Events

The Investigator (or sub-investigator) should follow-up subjects with AEs/SAEs, until the event has resolved or stabilized, and any abnormal laboratory values have returned to screening; or until there is a satisfactory explanation for the changes observed. In the case of death, if possible, a pathologist's full report should be supplied.

13.9 Pregnancy

If a female subject who has been exposed to the study medication becomes pregnant, the course and outcome of the pregnancy should be monitored and documented. Where possible, if a female partner of a male subject who has been exposed to the study medication becomes pregnant and the subject provides this information, then the pregnancy will be documented based on information provided by the subject.

A pregnancy that occurs in a subject who has been exposed to the study medication must be reported using the same timelines as an SAE, although pregnancy alone will not be classified as an SAE. If the outcome of the pregnancy or an event occurs during the course of pregnancy that involves an SAE (e.g., a congenital anomaly), then the SAE will also be reported.

Subjects who become pregnant while on study should be withdrawn from treatment, as described in Section 7.6.

13.10 Reference Safety Information

The reference safety information for this clinical study is the Oral Edaravone Investigator's Brochure. From the date of approval of oral edaravone in Japan, the package insert of oral edaravone will serve as the reference safety information.

13.11 Overdose

There is no known antidote for edaravone. Any signs or symptoms of a possible overdose will be treated supportively. In the case of an emergency, standard emergency procedures and supportive medical care will be given.

If the subject takes a dose which is greater or more frequent than that specified in the Protocol (with or without associated symptoms), this overdose is an AE and must be reported to the Sponsor or the designee on the AE eCRF.

If the overdose results in AEs that meet serious criteria, the SAE must be reported to Sponsor or the designee immediately or within 24 hours of awareness according to SAE reporting procedures (see Section 13.2).

13.12 After the date of marketing approval of oral edaravone

Data including AEs after the date of marketing approval in Japan will be handled as post-marketing clinical study data.

14 CASE REPORT FORM

14.1 Format of Case Report Form

In this study, the electronic CRF (eCRF) utilizing electronic data capture (EDC) system will be used. The original is defined as an eCRF confirmed by the investigator with the digital signature.

14.2 Identification of Documents Which Should Be Directly Recorded in the CRF and Handled as the Source Documents

The following data recorded in the eCRF will be handled as the source documents. However, when applicable information is recorded in a medical records etc., such medical records will be handled as the source documents.

- 1) AEs (seriousness, severity, outcome, date of outcome, relationship to the investigational product)
- 2) Date and reason of discontinuation, AE leading to discontinuation, courses and follow-up results after discontinuation
- 3) Comments from the investigator (or sub-investigator)

If any content is changed from the above, the sponsor and the investigator will specify the changes in writing, prior to the start of the study.

14.3 Notes for Data Entry in the CRFs

The investigator (or sub-investigator) or study coordinator will prepare eCRFs according to the following specifications. eCRFs will be prepared according to the “Guide to Changing or Correcting Case Reports” * provided separately by the sponsor.

* “Guide to Changing or Correcting Case Reports”: EDC operation manual and eCRF entry manual

- 1) Prior to data entry to the eCRFs, the sponsor will provide the investigator (or sub-investigator) or study coordinator with user IDs and passwords for user management. The investigator (or sub-investigator) and study coordinator will maintain the assigned user IDs and passwords themselves, and will not share them with any other persons. Data will be entered by the investigator (or sub-investigator) or by a study coordinator who is authorized for data entry.
- 2) eCRFs will be created for subjects receiving the investigational product.
- 3) The investigator can enter data in all fields of the eCRF. The sub-investigator is allowed to enter data in all fields of the eCRF, except for the digital signature.

A study coordinator is allowed to transcribe data from the source documents (e.g., medical records) to eCRFs, for data that requires no medical judgment.

- 4) When changing or correcting a recorded eCRF, the reason for the change or correction will be recorded in the form of electronic data.
- 5) The investigator will confirm that the eCRF is accurate and complete and that the audit trail and digital signature can be confirmed. After the confirmation, the investigator will enter the digital signature on the eCRF in the EDC system.
- 6) The investigator will maintain storage media (e.g., CD-R) that contains a copy of the eCRFs (that are checked by the investigator and stored in PDF files). The eCRFs will be accessible (via access rights in the EDC system) after the attachment of the digital signature, until the receipt of storage media (e.g., CD-R) from the sponsor that serves as a substitute copy.
- 7) If there are any discrepancies between the data entered in the eCRF and the source documents, the investigator will create a separate report detailing the reasons for the discrepancy, submit it to the sponsor, and retain a copy.

14.4 Time Points to Submit CRFs

The investigator (or sub-investigator) will promptly complete eCRF entry after completion of the specified tests/observations or assessment.

15 STATISTICAL METHODS AND PLANNED ANALYSES

The SAP will detail the implementation of all the planned statistical analyses in accordance with the protocol. The SAP will be prepared and finalized prior to fixing the data. If the analysis plan is revised or any ad-hoc analysis is implemented after fixing the data, Any deviations from the planned analysis will be described separately in the CSR.

15.1 Determination of Sample Size

The study sample size is not based on power and statistical considerations. This study serves as an extension to MT-1186-A03 and MT-1186-A04 (the Parent study) and as such will roll over subject to the current study. The total number of subjects enrolled will depend on the number of subjects who complete Week 96 of Study MT-1186-A03 or Week48 of Study MT-1186-A04 and are also eligible and consent to participate in this extension study.

Approximately 30 patients will potentially be enrolled in this study.

15.2 Analysis Sets

15.2.1 Safety Analysis Sets

The Safety Analysis Set (SAF) is defined as all enrolled subjects who received at least 1 dose of oral edaravone.

15.2.2 Study Medication Exposure

The duration of exposure in days will be calculated as follows:

date of last dose of oral edaravone –date of first dose of oral edaravone + 1

If the date of the last dose or the date of the first dose cannot be determined, then the duration calculation will not be completed. The duration of exposure will be summarized using descriptive statistics.

All exposure data will be listed. Interruptions and compliance are not considered for duration of exposure.

15.3 Statistical Analyses

15.3.1 General Considerations

The statistical analysis will be performed using SAS® Version 9.4 or higher.

Continuous variables will be summarized descriptively using the number of observations (n), mean, standard deviation (SD), median, minimum, and maximum. Categorical variables will be summarized using frequency counts and percentages.

All individual subject data will be listed.

15.3.2 Data Handling

15.3.2.1 Handling of Time Point Data in Analyses Performed by Measurement time Point (Analysis Visit Windows)

For the analyses performed for each measurement time point, the allowable range of data handling for the analysis will be specified as analysis visit window in the SAPs.

No data imputation will be performed using data from outside the allowable range. If multiple values are available within the allowable range for the endpoint in question, then the latest value will be analyzed.

15.3.2.2 Handling of Reference Values and Indeterminate Values for Clinical Laboratory Test Parameters

If laboratory test value or its reference is indeterminate due to a problem with the test sample, then this value will be handled as a missing value.

15.3.3 Statistical Analysis Method

15.3.3.1 Analysis of Demography and Other Baseline Characteristics

Demographic variables including age, sex, race, and ethnicity will be summarized using descriptive statistics or frequency with percentage.

15.3.3.2 Efficacy Analysis

15.3.3.2.1 ALSFRS-R Scores

The ALSFRS-R scores will be listed descriptively at each visit.

15.3.3.2.2 Death, Tracheostomy, or Permanent Assisted Mechanical Ventilation

The number and percentage of events for death, tracheostomy or permanent assisted mechanical ventilation (≥ 23 hours/day) will be listed at each visit.

15.3.3.3 Safety Analyses

TEAEs will be coded using the latest available version of the MedDRA and will be summarized in incidence tables by SOC and PT. The numbers and percentage of subjects with TEAEs will be calculated by SOC and PT. The following summaries will be presented:

- TEAEs by SOC and PT
- TEAEs by SOC, PT, and severity
- TEAEs by SOC, PT, and drug relationship

- TEAEs leading to discontinuation of study drug by SOC and PT
- TEAEs leading to death by SOC and PT
- TEAEs related to study drug by SOC and PT
- TEAEs related to study drug by SOC, PT, and severity
- Serious TEAEs by SOC and PT
- Serious TEAEs related to study drug by SOC and PT

For each of the summaries, multiple occurrences of the same event within a subject will be counted once in the summaries by SOC and PT; multiple occurrences of the same event within a subject will be counted once in the maximum severity category (severe > moderate > mild) and/or maximum study drug relationship category (reasonable possibility/no reasonable possibility). If severity or relationship is found to be missing the most severe occurrence will be imputed for that particular summary.

All AEs for each subject, including multiple occurrences of the same event, will be presented in a full comprehensive listing including subject number, severity, seriousness, action taken, outcome, relationship to study drug, onset/stop date and duration etc..

Duration of the AE and time to the AE occurrence from start of oral edaravone will be calculated and presented in days (duration = AE stop date – AE start date + 1 and time to AE occurrence = AE start date – The first administration date of study drug + 1).

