	
• TEAEs leading to death by SOC and PT• TEADRs by SOC and PT• TEADRs by SOC, PT, and severity• Serious TEAEs by SOC and PT• Serious TEAEs related to study drug by SOC and PT 
Data collected from other safety evaluations will be summarized descriptively and/or listed according to the data type and will include the following:
 
• Body weight;• 12-lead ECG;• Vital signs (including orthostatic);• C-SSRS

Mitsubishi Tanabe Pharma Group

Protocol: MT-1186-A-301

Abbreviation: EOS = end-of-study, ET = early termination.

- a. Subjects will receive oral edaravone 105 mg once daily dosing for 10 days out of a 14-day period, followed by a 14 day drug free period. Oral edaravone will be administered following an overnight fast and subjects must continue to fast at least 1 to 2 hours post-dose before the next meal (e.g, breakfast).
- b. Evaluations for EOS will be performed at an earlier date of either “commercial oral edaravone available at each study site” or “August 31st,2023”. When commercial oral edaravone is available at each study site, the investigator should ask subjects to visit the study site and complete their EOS visit. If the EOS visit is completed prior to Week 24, no tests or evaluations for Week 24 will be done.
- c. When the treatment is discontinued prior to completion of the study, the investigator should complete the ET evaluations within seven days after the discontinuation.

Figure 1 : Study Schema

Table 1 : Schedule of Activities

Assessment	Week (window)	1 (x): Based on Week 96 of MT-1186-A03 or Week 48 of MT-1186-A04. No re-tests or evaluations will be performed for MT-1186-A-301 study	24 (± 7D)	EOS/ET ^a (± 7D)
Cycle	1	7		
Visit	1	2	3	
Informed consent	X			
Eligibility criteria	X			
Demographics ^b	X			
Vital signs ^c	(X)	X	X	
Orthostatic vital signs	(X)	X	X	
Pregnancy test (urine)	X	X	X	
Full Physical examination ^{d1}	(X)			X
Routine physical examination ^{d2}		X		
12-lead ECG ^e	(X)	X	X	
Body weight	(X)	X	X	
Event of death, tracheostomy or permanent assisted mechanical ventilation ^f	(X)	X	X	
Hematology ^g	(X)	X	X	
Chemistry ^h	(X)	X	X	
Urinalysis ⁱ	(X)	X	X	
Dispense edaravone ^j	X	X		
ALSFRS-R	(X)	X	X	
C-SSRS	(X)	X	X	
IMP compliance ^k	(X)	X	X	
Adverse events	(X)	X	X	

Abbreviation: D = Day; ECG = Electrocardiogram; C-SSRS = Columbia–Suicide Severity Rating Scale; ALSFRS-R = ALS functional rating scale- revised; EOS = End-of-study; ET = early termination.

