8.1.2 End of Treatment/Early Termination (EOS/ET)

The assessment at Visit 3, EOS will be conducted for subjects who complete the open-label treatment period (earlier date when oral edaravone is commercially available at each site in Japan or August 2023), per the Schedule of Assessments (Table 1). If it becomes possible to prescribe commercially available oral edaravone at each site, subjects will be asked to visit the study site immediately at the end of the last cycle to evaluate EOS.

For subjects who terminate early from the study, assessments should be performed per the Schedule of Assessments (Table 1) within 7 days of study discontinuation.

Any unresolved AE or SAE will be followed up according to Section 13.8.

In the event that a subject elects not to return to the clinical site for the ET Visit, the Investigator must make every effort to contact the subject to review all AEs. In the event that a subject drops out of the study at any time, the reason for discontinuation must be fully documented in the source documents and the eCRF. The Investigator site personnel will document the AEs and any other assessments in the source documents and will make every effort to complete all required ET assessments.

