12.2 Dosing of Oral Edaravone

All subjects enrolled will receive 105 mg of oral edaravone, once daily, as specified in the protocol (administered once daily for 10 days out of 14, followed by a 14-day drug-free period) in each cycle. Treatment cycles will occur every 28 days.

The dose of edaravone should be taken after an overnight fast and subjects must continue to fast at least 1 to 2 hours postdose before the next meal (eg, breakfast).

A description of the oral edaravone and study medication dispensed is provided in Table 2.

Table 2: Investigational Product

Product Name	Edaravone
Dosage Form	Oral suspension
Unit Dose	105 mg
Route	Oral/PEG/RIG tube
Physical Description	Aqueous viscous suspension
Manufacturer	Mitsubishi Tanabe Pharma Corporation

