13 ADVERSE EVENT MANAGEMENT

All AEs and SAEs will be recorded in the source documents. All AEs and SAEs that occur from the time written ICF is obtained until the end of the Safety Follow-up Period will be recorded in the eCRF. Even if an AE is assessed by the Investigator as not related to IMP, its occurrence must be recorded in the source documents and eCRF. AEs will be classified as 'treatment-emergent' if they arise following the administration of IMP or if a predose AE increases in severity following dosing.

At each study visit, after the subject has had an opportunity to spontaneously mention any problems, the Investigator should inquire about the occurrence of AEs. The questioning should be open-ended and non-leading.

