7.1.3 Safety Assessments

7.1.3.1 Adverse Events

Adverse events will be coded according to the MedDRA version 25.0.

(1) Treatment Emergent Adverse Events/ Treatment Emergent Serious Adverse Events (TEAEs/TEsAEs)

An AE/SAE is classified as treatment emergent if it newly occurred after the first dose of investigational product or if a pre-dose event increases in severity following the first dose of investigational product.

(2) Adverse Drug Reaction

A TEAE is considered “adverse drug reaction” if it has been assessed as having a “reasonable possibility” in relationship to the investigational product.

(3) Time to Adverse Events

Time to Adverse Events occurrence (days) = AE start date – date of first administration in this study + 1

If the date of onset of an adverse event or the first administration is indeterminate, time to adverse events occurrence is not calculated.

(4) Duration of Adverse Events

Duration of Adverse Events (days) = AE stop date – AE start date + 1

If the adverse event is ongoing at the end of study, duration of adverse events is not calculated.

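### Do the TEAE percentages need a stated last day, given that the Safety Follow-up Period is never defined?

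*Protocol*

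**What the plan says.** **What is tabulated.** Protocol 15.3.3.3: "The numbers and percentage of subjects with TEAEs will be calculated by SOC and PT". SAP 6.1 sets the denominator as the analysis population, which SAP section 5 makes the SAF.

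**What counts.** SAP 7.1.3.1(1): "An AE/SAE is classified as treatment emergent if it newly occurred after the first dose of investigational product"; an event already present that worsens after that dose also counts. Protocol 13 has the same start, and neither document states an end. SAP section 1 gives the SAP precedence on analysis details.

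**What is recorded.**
- Protocol 13 covers events "from the time written ICF is obtained until the end of the Safety Follow-up Period will be recorded in the eCRF".
- Protocol 13.6 covers events "until the end of the safety Follow-up Period or the withdrawal of the subject from the study will be recorded".
- Protocol 13.7 has the same span for serious events: "All SAEs occurring from the time written ICF is obtained from a subject until the end of" that period, or withdrawal.

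No section gives the period a visit or a length. Section 13.6 also mentions a Final Follow-up period, likewise undefined.

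**When contact ends.** Protocol Table 1 and SAP 3.3 both end at EOS/ET, and the adverse event row is marked there. For completers, Protocol 8.1.2 says "subjects will be asked to visit the study site immediately at the end of the last cycle to evaluate EOS". For early stoppers, note c to the study schema says "the investigator should complete the ET evaluations within seven days after the discontinuation".

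**Exposure.** Both documents use last dose minus first dose plus 1 (Protocol 15.2.2, SAP 7.1.1.1).

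**The concern.** A percentage of subjects with an event depends on how long they are watched. Here the recording period ends at an undefined milestone, and the definition of treatment-emergent has no closing date to fall back on. SAP 7.2 sets windows for vital signs, ECG, weight, ALSFRS-R and C-SSRS, but not for adverse events.

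The way the study closed sharpens the worry. It stopped because commercial oral edaravone became available, and SAP 7.2 records that nobody reached Week 24. If sites kept recording new events after EOS, some could arise on commercial drug and still be counted here. With short follow-up, a few extra weeks would be a sizeable share of the total.

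The exposure summary also stops at the last dose, while events in the drug-free days before EOS are counted. A reader who sets one table beside the other could take the observation period to be shorter than it was.

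**Working it through.** **1. Does the counting rule leave a choice?** No. Every recorded event that is new or worse after the first dose is counted, over the SAF. Two analysts with one database get one table. The uncertainty lies in what sites record, which is a matter of Protocol 13, 13.6 and 13.7.

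**2. Where does recording end in practice?**

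| Source | End point implied |
|---|---|
| Protocol Table 1, SAP 3.3 | Last scheduled adverse event assessment at EOS/ET |
| Protocol 8.1 | Treatment, EOS/ET and unscheduled visits only; no later period |
| Protocol 8.1.2, 13.8 | After EOS/ET, unresolved events are followed up |
| Protocol 8.1.2, no ET visit | Investigator must try to reach the subject and review all events |
| Protocol 16.5 | Study ends at the last subject's last visit |
| Protocol 13.6, 13.7 | Undefined follow-up period, or withdrawal |

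All but the last row point to EOS/ET. The telephone contact in note a of both schedules concerns the subject's condition and sets no end to recording. What remains is withdrawal against an ET visit up to 7 days later.

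**3. How much could that week matter?** The plan states no figure to reproduce, so this is an illustration.

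- Inputs from Protocol 4.2, Study MT-1186-A01 over 48 weeks: any TEAE 175/185 = 94.6%, serious TEAE 48/185 = 25.9%.
- Assumptions: constant rate, at A01's level or half of it; 3 cycles = 12 weeks; 30 subjects.
- Weekly rate r = −ln(1 − p)/48. Any TEAE: −ln(1 − 175/185)/48 = 0.0608. Serious: −ln(1 − 48/185)/48 = 0.00626.
- Percentage by week t = 1 − exp(−r·t).

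| | 12 weeks | 13 weeks | Difference | Of 30 subjects |
|---|---|---|---|---|
| Any TEAE, A01 rate | 51.8% | 54.6% | 2.8 points | 0.8 |
| Any TEAE, half rate | 30.6% | 32.6% | 2.1 points (unrounded) | 0.6 |
| Serious TEAE, A01 rate | 7.2% | 7.8% | 0.6 points | 0.2 |

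This overstates the effect, because it gives the extra week to all 30 subjects when only early stoppers have the gap.

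**4. What about a longer tail?** Four further weeks would take any TEAE from 51.8% to 62.2% (3.1 of 30), or from 30.6% to 38.5% at half rate (2.4 of 30). The four weeks are an assumption with no source in either document, and neither schedule has a contact after EOS/ET at which such events would be collected. With recording to EOS/ET, the shift is zero.

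**5. Does the exposure mismatch affect a planned result?** Dosing is "administered once daily for 10 days out of 14, followed by a 14-day drug-free period" in a 28-day cycle, so after k cycles the last dose falls on day 28(k − 1) + 10 to 28(k − 1) + 14. If EOS is at day 28k, the gap is 28 − 14 = 14 to 28 − 10 = 18 days. For k = 3, exposure is 66 to 70 of 84 days, or 79% to 83%. This relies on the end-of-cycle timing in Protocol 8.1.2. Note b to the study schema ties EOS to commercial availability or August 31st, 2023, which need not be a cycle end, so the gap is not fixed. More to the point, neither document plans an exposure-adjusted rate, so the ratio enters no output.

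**The case for a change.** The strongest opposing argument concerns the sickest subjects. Protocol 7.6 withdraws anyone who needs tracheostomy or permanent ventilation. Read literally, 13.6 and 13.7 let recording stop at that moment, while Protocol 13 and Table 1 keep it open to ET. A serious event or death in that interval is inside one reading and outside the other. Moreover, SAP section 10 restricts the summary of death, tracheostomy and ventilation to EOS/ET because of when those data are collected, so the authors could have treated adverse events the same way.

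The textual conflict stands. Its effect is small, for three reasons. Protocol 11.2 calls for ET assessments after such an event, and 7.6 and 8.1.2 tell sites to document adverse events and make every effort to complete ET, so the operating instruction runs to ET. Death, tracheostomy and ventilation are also captured in their own right and summarised under SAP 8.1.6. And SAP 8.2.1 lists all TEAEs, with Protocol 15.3.3.3 asking for onset and stop dates, so a late event is visible.

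Separating events that began on commercial drug would need a start date for that drug, and neither schedule shows one being collected. A cut-off added now would post-date the 20 Sep data review meeting and so would be chosen with the data in view. Observation time in person-years would be a reasonable extra, but it corrects no planned result.

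**Conclusion.** The wording gap is real: an undefined follow-up term, withdrawal and ET given as different ends, and no last day for treatment-emergence. It is missing detail that the schedules fill sensibly. Following the plan as written, events are assessed to EOS/ET, every recorded post-dose event is counted once per subject over the SAF, and the descriptive tables are sound.

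If recording ended at EOS/ET, as both schedules indicate, nothing changes. If some sites stopped at withdrawal, the difference is at most about a week for those subjects, worth under one subject in 30 even when applied to everyone. That size rests on a constant rate borrowed from A01 (or half of it), an assumed 12 weeks of follow-up and the planned enrolment of about 30. Only new events actually recorded after EOS/ET could make it larger, and neither schedule provides a visit for collecting them. Ending exposure at the last dose is a normal definition, stated alike in both documents. With one arm, no hypothesis test and no exposure-adjusted rate, no conclusion turns on this point.
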